### **5.2.4 Dermatitis Assessment**

Proportion of patients who develop moderate erythema, the proportion of patients who develop dry desquamation and the proportion of patients who develop moist desquamation (according to eCRF) will be analyzed in a similar manner to the analysis in Session 5.2.2.

### **5.2.5 Patient-reported Outcomes (Skindex-16)**

The Skindex-16 quality-of-life tool will be used to assess patient responses to skin toxicity during and after radiation therapy. The Skindex-16 is a short 16-item patient-completed assessment using numerical analogue scales (0=never bothered to 6=always bothered). Responses to the Skindex-16 are categorized into three subscales: symptom, emotional and functional. Refer to Appendix C for the Skindex-16 assessment. The Skindex-16 assessment will be scored using the tool's scoring algorithm which averages all responses for the total Skindex-16 score. Subscale scores will be calculated as follows: symptom subscale as the mean of questions 1–4, emotional subscale as the mean of questions 5–11 and functional subscale as the mean of questions 12–16.

Descriptive statistics (means and standard deviation, minimum, median, and maximum) will be summarized for the total score and each subscale score for the available patient-reported data, by treatment groups. Analysis of variance (ANOVA) will be used to compare the total and subscale scores among the three treatment groups.

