7.5. Schedules of Assessments

[Table 3](#) lists the overall schedule of assessments for the study.

Table 3: Overall Schedule of Assessments

Assessment	Screening Period	Randomization and Run In Period	Day 1 of Radiation Treatment	Concurrent with RT					Last day of RT	After RT	Last day of Study Drug	ET / Follow-up
				4 ^d	5 ^d	6 ^d	7 ^d	8 ^e				
Study Visit	1 ^a	2 ^b	3 ^c	RT WK 2	RT WK 3	RT WK 4	RT WK 5	RT WK 6	Last Day of RT ^d	Post-RT WK 1	Post-RT WK 2 / End of Study Drug Administration	Post-RT WK 6 / ET / Follow-up Visit
Visits or Visit Procedures may fall within a window of ± 2 days for a total of 2 days ⁱ	Up to 45 days	Randomization Visit - First Day of Study Lotion Application for Run-In Period 7 days prior to RT ^b	RT WK 1 ^c									
Informed consent	X											
Inclusion/ Exclusion	X	X										
Demographics and baseline disease characteristics	X											
Fitzpatrick skin type	X											
Prior and Concomitant medications	X	X	X				X		X		X	X
Medical history ^j	X											
Height	X ^k											
Weight and BMI	X ^k					X			X			X
Vital signs	X ^k					X			X		X	X
Physical exam	X ^k											X
Smoking status	X											
Chest wall separation	X											
Measurement of radiation treatment skin surface area ^l (Prior to RT)	\leftarrow X ^l \rightarrow											
Breast volume (lumpectomy and breast-conserving surgery patients) ^m	X											
Randomization		X										
Pregnancy test WOCBP ⁿ	X ^t	X			X					X		X
Dispense/ Weigh study drug ^o		X			X			X				
Study drug application/diary ^p	\leftarrow X \rightarrow											
Collect / Weigh study drug					X			X			X	
Radiation treatment ^q			X	X	X	X	X	X				
Dermatitis assessment ^r			X	X	X	X	X	X	X		X	X
Skindex-16 assessment ^s			X						X		X	X
Adverse event collection		X	X	X	X	X	X	X	X	X	X	X
Clinical chemistry	X ^t				X			X			X	X
Hematology	X ^t					X			X		X	X
Urinalysis and microscopy	X ^t					X			X		X	X
PK sample ^u			X		X				X		X	X
Photograph collection				X ^v					X ^v		X	X
End of Study												X

^a The Screening Period (Visit 1) may last up to 45 days prior to Randomization (up to 52 days prior to Day 1 of RT).

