^b Visit 2 (7 days prior to radiation treatment) is the day of randomization and application of the first dose, and must occur at least 5 and no more than 9 days prior to the first day of radiation treatment. If the start of radiation treatment is delayed, patients should continue administering study drug twice daily until the first dose of radiation up to a maximum of 14 days. If the time from randomization to first dose of radiation exceeds 14 days, the medical monitor should be contacted to decide on an appropriate action. Patients may be randomized after meeting the inclusion / exclusion criteria and before study drug lotion is first administered as long as patients apply study drug lotion for at least 5 days prior to the first day of radiation treatment. Patients with either morning or afternoon randomizations may apply lotion in the clinic and again before bedtime for two doses on that day.

^c Visit 3 should occur on the day of the first radiation treatment. If radiation treatment is in the morning, the radiation treatment will be the third to last procedure (radiation treatment > study drug application > PK). If radiation treatment is in the afternoon, radiation treatment will be the second to last procedure, and the last procedure will be PK, as study drug will have been applied at least 4 hours prior to radiation treatment.

^d Study visits during radiation treatment therapy must occur weekly beginning with Day 1 of radiation treatment.

^e At the end of radiation treatment, patients must complete Visit 9 assessments. Visit 9 must be the last day of the 10 – 16 Gy boost. Visit 8 is needed for patients who require radiation therapy for 6 weeks. If radiation therapy is extended longer than 6 weeks, then assessments at Visit 8 should be repeated weekly until the end of radiation visit (Visit 9). A weekly study visit should not be performed if the visit falls 1 or 2 days prior to the last day of radiation (Visit 9), or 1-2 days after the last day of radiation.

^f Visit 10 should occur approximately 1 week (7 calendar days) after the completion of radiation therapy (Visit 9).

^g Visit 11 should occur approximately 1 week (7 calendar days) after Visit 10 (*i.e.*, 2 weeks after the completion of radiation therapy).

^h Follow-up visit will occur approximately 4 weeks after the final study drug application. These procedures should be performed at the end of study and for early termination.

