^r Radiation dermatitis assessments must be performed PRIOR to initiation of that day's radiation treatment, and only by a trained evaluator. If radiation treatment is delayed or extended, dermatitis assessments should be performed weekly until the end of radiation treatment.

^s The Skindex-16 must be completed prior to initiation of that day's radiation treatment.

^t Screening lab assessments (described in Section 9.8 for [chemistry](#), [hematology](#), [urinalysis](#), and [serum pregnancy tests](#)) should be drawn ≤ 14 days prior to randomization in order to have current values for inclusion/exclusion assessment.

^u A single PK collection will be obtained on Visit 3, Visit 6, Visit 9, Visit 11 and Visit 12. If patients are to receive a morning radiation treatment on any of these visits, the PK sample should be drawn after RTA 408 Lotion or Vehicle Lotion application, which occurs after the completion of radiation treatment. If patients are to receive an afternoon radiation treatment on any of these visits, the PK sample should be drawn after the radiation treatment.

^v Optional photographs may be collected at Sponsor-qualified sites. On Day 1 of radiation treatment and the last day of radiation treatment, photographs must be collected prior to radiation treatment.

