#### **3.3 Strata and Covariates**

Randomization is stratified by smoking status (smoker or ex-smoker versus non-smoker) and breast cancer treatment prior to radiation therapy (full mastectomy versus partial mastectomy or lumpectomy).

Smoking status and breast cancer treatment prior to radiation therapy will be used as covariates in the primary efficacy analysis.

No other covariates will be considered for the primary analysis. However, other covariates may be considered in a post hoc manner.

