#### **3.7.2 Definition of Study Baseline**

Unless otherwise noted, study baseline is defined as the last observation obtained prior to administration of the first dose on Study Day 1.

Change from baseline is defined as post-baseline assessment minus baseline assessment. The baseline value will not be used to impute the post-baseline values.

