- q Planned radiation treatment must be no more than 7.5 weeks.
- r Radiation dermatitis assessments must be performed PRIOR to initiation of that day's radiation treatment, and only by a trained evaluator. If radiation treatment is delayed or extended, dermatitis assessments should be performed weekly until the end of radiation treatment.
- s The Skindex-16 must be completed prior to initiation of that day's radiation treatment.
- t Screening lab assessments for [chemistry](#), [hematology](#), [urinalysis](#), and [serum pregnancy tests](#) should be drawn  $\leq 14$  days prior to randomization in order to have current values for inclusion/exclusion assessment.
- u A single PK collection will be obtained on Visit 3, Visit 6, Visit 9, Visit 11 and Visit 12. If patients are to receive a morning radiation treatment on any of these visits, the PK sample should be drawn after RTA 408 Lotion or Vehicle Lotion application, which occurs after the completion of radiation treatment. If patients are to receive an afternoon radiation treatment on any of these visits, the PK sample should be drawn after the radiation treatment.
- v Optional photographs may be collected at Sponsor-qualified sites. On Day 1 of radiation treatment and the last day of radiation treatment, photographs must be collected prior to radiation treatment.

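### The Skindex-16 ANOVA in SAP 5.2.5 names no visit, no within-patient structure, no stratification factors and no contrast with vehicle

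*SAP*

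**What the plan says.** SAP 5.2.5 defines the Skindex-16 total and three subscale scores, plans descriptive statistics by arm, and gives the comparison in one sentence: "Analysis of variance (ANOVA) will be used to compare the total and subscale scores among the three treatment groups". It does not say which visits enter, how several scores from one patient are handled, which covariates are used, or how an arm is compared with vehicle. Protocol 13.2.2.2 describes the instrument but gives no analysis.

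Table 3 in Protocol 7.5, repeated in SAP Appendix 1, schedules the questionnaire at Visit 3 (Day 1 of radiation), Visit 9 (last day of radiation), Visit 11 (two weeks later) and Visit 12 (follow-up). On timing within the day: "The Skindex-16 must be completed prior to initiation of that day's radiation treatment". The Visit 3 score therefore precedes radiation. It does not precede treatment. Footnote b of the same table says of Visit 2 that it "is the day of randomization and application of the first dose, and must occur at least 5 and no more than 9 days prior"; the interval is counted back from the start of radiation. In SAP 3.7.2, "study baseline is defined as the last observation obtained prior to administration of the first dose on Study Day 1", and no Skindex-16 is scheduled that early.

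On the strata, SAP 3.3 says: "Randomization is stratified by smoking status (smoker or ex-smoker versus non-smoker) and breast cancer treatment prior to radiation therapy". It then assigns them to one analysis: "Smoking status and breast cancer treatment prior to radiation therapy will be used as covariates in the primary efficacy analysis".

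Elsewhere the SAP is more specific. Section 5.1 uses a longitudinal mixed model. Section 5.2.1 uses an ANCOVA that adjusts for site, both strata and weeks of drug use, with differences from vehicle and 95% CIs, and Section 5.2.3 refers back to it. Section 5.2.5 has no such cross-reference.

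**The concern.** The SAP uses the word ANCOVA where it wants adjustment and names vehicle contrasts where it wants them, so the bare ANOVA in 5.2.5 cannot be assumed to be shorthand for the same thing. The endpoints in 5.2.1 and 5.2.3 yield one value per patient. Skindex-16 yields up to four, so the test cannot be programmed without a decision that the SAP does not record.

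Three things are at stake. First, if each visit is tested separately, there are 3 later visits x 4 scores = 12 tests with no rule for which one carries the conclusion, and the information in the strata is unused. Second, if the visits were put into one ANOVA, the standard error would be too small and the pre-radiation score would form part of the outcome. Third, a three-group F test gives no estimate or interval for 3%, 0.5% or pooled RTA 408 against vehicle, which are the comparisons that SAP 3.5 sets out for the trial.

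**Working it through.** **Inputs.** 59 patients per arm, 177 in total (Protocol 7.2; 3 x 59 = 177). The public text shows no Skindex-16 SD, effect size, correlation or power, so there is no stated figure to reproduce. Assumed here: scores in SD units, two-sided alpha 0.05, strata R-squared 0.02 to 0.10, correlation between a patient's scores 0.3 to 0.7, and correlation of Visit 3 with later scores 0.1 to 0.6.

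**1. One ANOVA per visit.** Each patient contributes one score, so the test is valid. The unadjusted SE of a difference between two arms is sqrt(2/59) = 0.184 SD.

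Adjusting for the strata multiplies the SE by sqrt(1 - R²). Because stratified randomization balances these factors, an ANOVA that ignores them overstates its error. The chi-square approximation to the three-group test then gives a true size of 0.05^(1/(1 - R²)).

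| Assumed R² | SE factor | SE reduction | Size of unadjusted test |
|---|---|---|---|
| 0.02 | 0.990 | 1.0% | 4.7% |
| 0.05 | 0.975 | 2.5% | 4.3% |
| 0.10 | 0.949 | 5.1% | 3.6% |

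For an assumed difference of 0.5 SD between two arms, power rises from 77.5% unadjusted to 78.3%, 79.6% and 81.7% across these rows.

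**2. Scores stacked as if independent (one possible reading, not stated).** With m scores per patient and correlation rho, the true variance of an arm mean exceeds the naive one by D = 1 + (m - 1) x rho. The nominal 5% three-group test then has size of about 0.05^(1/D).

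| rho | D, m = 3 | Size, m = 3 | D, m = 4 | Size, m = 4 |
|---|---|---|---|---|
| 0.3 | 1.6 | 15% | 1.9 | 21% |
| 0.5 | 2.0 | 22% | 2.5 | 30% |
| 0.7 | 2.4 | 29% | 3.1 | 38% |

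A simulation with m = 3, 59 per arm, equal visit means and 4,000 trials per correlation gave 15.0%, 23.3% and 29.0%. The single-visit test in the same runs gave 5.6%, 5.6% and 4.9%, consistent with 5% (Monte Carlo SE sqrt(0.05 x 0.95/4000) = 0.3 percentage points).

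These sizes assume equal means across visits. With no visit term, differences between visit means go into the residual. If their variance is v, relative to the within-visit variance, the size becomes 0.05^((1 + v)/D), which is smaller. This matters most for m = 4, where a pre-radiation score is mixed with end-of-radiation scores.

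**3. Adjusting for the Visit 3 score.** The SE factor is sqrt(1 - rho²).

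- rho 0.1: 0.995, a reduction of 0.5%
- rho 0.3: 0.954, a reduction of 4.6%
- rho 0.5: 0.866, a reduction of 13.4%
- rho 0.6: 0.800, a reduction of 20%

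The possible gain is larger than from the strata, but Visit 3 follows randomization and about a week of lotion. If lotion had already shifted that score by an assumed 0.1 SD, adjusting for it would move the estimated effect by rho x 0.1, which is 0.03 SD at rho 0.3 and 0.07 SD at rho 0.7.

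**The case against.** The strongest defence is that the SAP is silent rather than wrong. A separate ANOVA at each scheduled visit fits its words, is valid, and if anything errs on the conservative side. That stands. A reader might infer from 5.2.5 that correlated scores will be treated as independent, that the error rate is therefore inflated, or that the interval will be too narrow. The documents support none of these: stacking is nowhere stated, and 5.2.5 plans no confidence interval.

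A reader might also infer that the plan discards a Skindex-16 baseline. It does not. No score is scheduled before first dose, so under SAP 3.7.2 Visit 3 is not a baseline, and adjusting for it could remove part of a treatment effect. Pre-radiation scores may also lie near the bottom of the scale, where their correlation with later scores, and hence the gain, could be small.

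The strata and the pooled arms are not wholly absent. SAP Section 5 plans efficacy analyses within subsets defined by smoking status and prior breast cancer treatment, and a pooled RTA 408 column in summaries. Subset results and a summary column are neither covariate adjustment nor an estimated contrast with vehicle.

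Finally, SAP 5.2 asks for caution with secondary p-values, and SAP 2.2.1 leaves Skindex-16 out of its list of secondary efficacy endpoints. The caution concerns multiplicity and does not tell the programmer which scores to test. As for the list, SAP 1.1.2 makes Skindex-16 a secondary objective and 5.2.5 sits under secondary efficacy.

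**Conclusion.** The point holds as underspecification with an available improvement. The planned ANOVA leaves visits, within-patient correlation, strata and vehicle contrasts undefined for the only patient-reported outcome, while the same SAP specifies such features for other endpoints.

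On the by-visit reading the cost is modest: about 1% to 5% of the SE from the unused strata, under an assumed R-squared of 0.02 to 0.10, plus the absence of any estimate against vehicle. The inflated sizes of 15% to 29% for three visits or 21% to 38% for four apply only if scores are stacked. They rest on assumed correlations of 0.3 to 0.7 and equal visit means, and show what the wording leaves open rather than what the plan will do. The gain from adjusting for Visit 3, 0.5% to 20% of the SE for an assumed correlation of 0.1 to 0.6, cannot be established from the documents.

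Secondary endpoints have no formal type I error control, and the primary analysis and its conclusion are unaffected.

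**What to change.** Before database lock, replace the ANOVA sentence in SAP 5.2.5 with a repeated-measures mixed model for the total and each subscale score:

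- Outcome: scores at Visits 9, 11 and 12, with within-patient correlation modelled (for example, an unstructured covariance).
- Fixed effects: treatment, visit, treatment by visit, smoking status and prior breast cancer treatment.
- Reported results: 3%, 0.5% and pooled RTA 408, each against vehicle, as adjusted mean differences with 95% CIs at each visit.
- Sensitivity analysis, labelled as such: the same model with the Visit 3 score added, noting that this score follows randomization and about a week of lotion.

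The new text should also say whether the worst-observation imputation in SAP 3.6 applies here, since 5.2.5 refers to available data.

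The cost is a paragraph of SAP text and a few lines of code, with no new data or visits. A future design could schedule a Skindex-16 before first dose, which would supply a true baseline covariate.

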## **6. PHARMACOKINETIC ANALYSIS**

Descriptive statistics will be summarized for RTA 408 plasma concentration by treatment group overall and by patient subsets of interest.

## 7. SAFETY ANALYSIS

Safety data (including AEs, laboratory data, vital signs, electrocardiogram [ECG] data, echocardiogram data, and physical examinations) will be listed and summarized for patients in the safety analysis set. All safety data collected on or after the date of the first dose of study drug through completion of the study will be summarized by treatment.

The CRF nominal study visits will be used for all safety analyses. Unscheduled visits will be reflected in summarization of changes to worst post-baseline measures where appropriate.

### 7.1 Adverse Events

New or worsening radiation dermatitis signs/symptoms should not be captured as individual AEs, but rather are captured in the Dermatitis Assessment documentation as these signs/symptoms are being assessed as study endpoints.

AEs will be summarized by treatment as defined by the safety analysis set.

#### 7.1.1 General Considerations for Analysis of Adverse Events

General considerations for AE summaries and calculations are:

- Multiple events by preferred term (PT) and system organ class (SOC) will be counted once only per patient for each treatment.
- For summaries by severity, only the most severe event will be counted per patient for each treatment.
- For summaries by relationship, only the most related event will be counted per patient for each treatment.
- An AE with a missing resolution date or incomplete date that is not identified as continuing will be assumed to be continuing and no duration will be calculated.
- AEs will be summarized by the highest dose received.
- Only treatment-emergent adverse events (TEAEs) will be included in summaries.

#### 7.1.2 Adverse Event Dictionary

AEs will be coded using MedDRA® (Medical Dictionary for Regulatory Activities) version 16.0 or higher. Tables and listings will present data at the SOC and PT level.

#### 7.1.3 Treatment-Emergent Adverse Events

##### 7.1.3.1 Definition of Treatment-Emergent

Treatment-emergent adverse events are events that either:

- Date of onset on or after the date of the date of first dose and not more than 30 days after the date of the last dose of study drug, or
- Had no recorded date of onset with a stop date after the first dose of study drug, or
- Had no recorded date of onset or stop date

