8.4.1. Patient Discontinuation Criteria

Discontinuation refers to a patient stopping administration of study drug. Reasons for study drug discontinuation include the following:

- Occurrence of an adverse event (AE) or change in medical status that leads the investigator to be concerned about the patient's welfare
- Noncompliance with study procedures
- Pregnancy during the study
- Investigator unblinding of patient

Patients who are discontinued from study drug should still attend all study visits and undergo all study assessments, if possible.

The CTCAE version 4.03 will be used to define patient stopping criteria for systemic adverse events, except where related to transaminase laboratory values. The criteria for a stopping criteria for adverse events related to transaminase laboratory values will be defined using the FDA Guidance for Industry titled "Drug-Induced Liver Injury: Premarketing Clinical Evaluation" (July 2009) rather than CTCAE.

The determination stopping criteria will be defined in each patient as all toxicity \geq Grade 3 (using CTCAE, version 4.03), except as noted below:

- Grade \geq 3 skin toxicity, with the patient allowed to continue at the discretion of the investigator;
- Nausea and vomiting will be considered stopping criteria if Grade 3 toxicity persists after optimal medical therapy.

Any hepatobiliary disorders of \geq Grade 2 (from CTCAE, version 4.03, pages 24 – 25) will be considered adequate stopping criteria. Note that laboratory measurements are included in a separate section of the CTCAE.

Changes in ALT, AST, and total bilirubin levels must meet one of the following criteria to be considered a DLT:

- ALT or AST $>$ 8X ULN
- ALT or AST $>$ 5X ULN for more than 2 weeks
- ALT or AST $>$ 3X ULN and (total bilirubin $>$ 2X ULN or INR $>$ 1.5)
 - (Repeat testing every 72 to 96 hours until transaminase levels are below three times the ULN for at least one week or patient withdraws consent.)
- ALT or AST $>$ 3X ULN with the appearance of fatigue, nausea, vomiting, right upper quadrant pain or tenderness, fever, rash, and/or eosinophilia ($>5\%$)
 - (Repeat testing every 72 to 96 hours until transaminase levels are below three times the ULN for at least one week or patient withdraws consent.)

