12.2. Adverse and Serious Adverse Events

12.2.1. Definition of Adverse Events

12.2.1.1. Adverse Event

An adverse event (AE) is defined as any untoward medical occurrence in a patient regardless of its causal relationship to study treatment. An AE can be any unfavorable and unintended sign (including any clinically significant abnormal laboratory test result), symptom or disease temporally associated with the use of the study drug, whether or not it is considered to be study-drug related. Included in this definition are any newly-occurring events or previous condition that has increased in severity or frequency since the administration of study drug.

New or worsening radiation dermatitis signs/symptoms should not be captured as individual AEs, but rather are captured in the Dermatitis Assessment documentation as these signs/symptoms are being assessed as study endpoints. Thus, if investigators seek to enter “radiation dermatitis”, “erythema”, “desquamation” or other signs/symptoms of radiation dermatitis as adverse events, they should first discuss the signs/symptoms with the medical monitor. The investigator in coordination with the medical monitor will determine how these signs/symptoms are to be recorded.

All AEs that are observed or reported by the patient during the study (from the time of first dose until the final visit indicated in [Table 3](#)) must be reported, regardless of their relationship to study drug or their clinical significance.

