### 7.1.3.2 Incomplete Dates

If the date of onset is incomplete, then the month and year of onset (or year alone if month is not recorded) determines whether the event is treatment-emergent. The event is treatment-emergent if the month and year of onset (or year of onset) of the event is:

- The same as or after the month and year (or year) of the first dose of study drug, and
- The same as or before the month and year (or year) of the date of the last visit.

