#### 7.1.6.1 Summaries of Adverse Events

Treatment-emergent AEs will be summarized by treatment at onset of the AEs. For each treatment, SOC, and PT, the number and percentage of patients reporting an event will be calculated. In summary tables, SOC will be presented alphabetically and events within SOC will be presented by decreasing frequency count based on the number of events in the total group.

Summary tables (number and percentage of patients) of AEs (by SOC and PT) will be provided by treatment as follows:

- All treatment-emergent AEs
- All treatment-emergent related AEs (probably or possibly related)
- All treatment-emergent AEs by severity
- All treatment-emergent serious adverse events (including deaths)
- All treatment-emergent adverse events leading to discontinuation of study drug

Listings will be provided showing:

- All AEs

- Serious adverse events (including deaths)
- AEs leading to discontinuation of study drug

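### The AE tables stop 30 days after last dose, although the SAP promises safety summaries through study completion and applies a later cut-off when the onset day is missing

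*SAP*

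**What the plan says.** **Collection.** Protocol 12.2.1.1 collects AEs "from the time of first dose until the final visit indicated in" Table 3, whatever their relationship to study drug; Protocol 12.2.1.2 does the same for SAEs. On patients who stop lotion, Protocol 8.4.1 says: "Patients who are discontinued from study drug should still attend all study visits and undergo all study assessments, if possible". SAP 1.2.2 repeats this.

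**Reporting, general rule.** SAP 7 states that safety data from the first dose "through completion of the study will be summarized by treatment".

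**Reporting, specific rules.** SAP 7.1.1: "Only treatment-emergent adverse events (TEAEs) will be included in summaries". SAP 7.1.3.1 makes a dated onset treatment-emergent if it is on or after first dose and "not more than 30 days after the date of the last dose of study drug". All five AE tables in SAP 7.1.6.1 carry the treatment-emergent label, including the one for SAEs and deaths. The listings of all AEs and of SAEs do not.

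**Incomplete dates.** Under SAP 7.1.3.2 an onset lacking the day, or the day and month, has this upper limit: "The same as or before the month and year (or year) of the date of the last visit". There is no 30-day cap. Under SAP 7.1.3.1 an event with no onset date is treatment-emergent if it stopped after first dose or has no stop date.

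**The concern.** SAP 7 cannot be programmed together with 7.1.1 and 7.1.3.1. The general section wants everything through study completion, and the specific sections cut at 30 days after last dose. The SAP governs over the protocol (SAP 1) but does not rank its own sections, so the programmer must choose. The specific rules define the tables and would probably win.

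The incomplete-date rule adds an anomaly: a poorly dated late event is tabulated, and the same event with a complete date is not. A 30-day window is a familiar convention, but that does not explain why losing the day of onset should lengthen it.

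Evaluating safety is a primary objective (Protocol 6.1, SAP 1.1.1). What is at stake is whether new AEs and SAEs arising late in the follow-up of patients who stopped lotion early reach any by-arm AE table.

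**Working it through.** **1. The plan's own calendar.** Application period: 1 + 6 + 2 = 9 weeks (8 with 5 weeks of radiation), as in Protocol 7.1. Follow-up visit: 2 + 4 = 6 weeks after radiation, matching the post-RT week 6 label in Table 3. Both reproduce.

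**2. Completers.** Visit 12 is 28 days after last dose, or 26 to 30 with the 2-day allowance. All of these are within 30 days, so essentially nothing is lost.

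**3. Timeline for early stoppers.** Inclusion criterion 3 gives 23 to 28 fractions before the boost (46/2 = 23; 50.4/1.8 = 28). The boost is 10 to 16 Gy. Its fraction size is not stated; at an assumed 2 Gy it adds 5 to 8 fractions, for a total of 28 to 36. At five fractions a week, 28, 31 and 36 fractions span 38, 43 and 50 calendar days. First dose is Day 1 and radiation starts on Day 8.

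- End of radiation = 7 + span: Day 45, 50 or 57.
- Planned last dose = end of radiation + 14: Day 59, 64 or 71.
- Visit 12 = planned last dose + 28: Day 87, 92 or 99.

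**4. Uncounted days if the patient is followed to post-RT week 6.** Uncounted = max(0, Visit 12 day − (stop day + 30)).

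| Lotion stops | Window closes | 28 fractions | 31 fractions | 36 fractions |
|---|---|---|---|---|
| Day 15 | Day 45 | 42 | 47 | 54 |
| Day 22 | Day 52 | 35 | 40 | 47 |
| Day 29 | Day 59 | 28 | 33 | 40 |
| Day 36 | Day 66 | 21 | 26 | 33 |

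For the Day 22 stop with 31 fractions, 92 − 52 = 40 of the 92 − 22 = 70 days after stopping are uncounted.

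**5. The same stop if the final visit follows the patient's own last application (Table 3, footnote h).** The final visit falls at stop + 28, inside stop + 30, so 0 days are uncounted. If the patient also attends Visit 11 on its radiation-based date (Day 64), events up to then can be reported and 64 − 52 = 12 days are uncounted.

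**6. The two date rules on one event.** First dose 1 September, last dose 22 September, SAE onset 6 November (45 days after last dose), final visit 30 November.

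- Full date: the limit is 22 October, so the event is not treatment-emergent and is in no AE table.
- Day missing (November only): not before September and not after November, so it is treatment-emergent and tabulated.

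**7. Number of patients.** The documents give no early-stopping rate. As an assumption only, 5% to 20% of 177 is about 9 to 35 patients (8.85 to 35.4). These are patients who could have a gap, not patients with a lost event; no late event rate is given either.

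**The case against.** **Deaths and SAEs do not vanish from the report.** A reader might infer that they do. Death is a reason for study termination (SAP 1.2.3), and SAP 4.1 tabulates termination reasons by randomized arm, so on-study deaths are counted. Late SAEs remain in the listings. This stands: the loss is from the AE tables only.

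**The test is on onset.** A death more than 30 days after last dose stays in the tables if the event began inside the window. This also stands.

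**Bias in favour of the worse-tolerated arm is not shown.** A reader might infer it because the gap falls on early stoppers. But an AE that leads to stopping begins while lotion is in use, so it is treatment-emergent and has its own table. Only new events starting more than 30 days later drop out, after a topical product whose Phase 1 plasma levels were near or below the quantitation limit (Protocol 5.1). Without stopping rates or late event rates by arm, no direction can be claimed.

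**The size depends on one reading of follow-up.** Protocol 8.4.1 asks for continued attendance only where possible. Footnote h places the follow-up visit four weeks after the final application and uses the same procedures for early termination. Protocol 9.5.1 implies that early-termination procedures follow drug discontinuation generally, and Protocol 9.7.3 takes pregnant patients out of the study. The 40-day figure is therefore conditional.

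**A 30-day window is a legitimate choice, and counting uncertain dates can be a cautious default.** Both are fair. Neither removes the conflict with SAP 7, or the result that the better-dated event is the one left out.

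**Conclusion.** The point holds as an internal inconsistency in the SAP with a limited consequence. For a patient who stops lotion early and stays under observation, a new, fully dated AE or SAE with onset more than 30 days after last dose enters no AE table. SAP 7 says it should be summarized, and SAP 7.1.3.2 would count it if its day were missing. Completers are essentially unaffected.

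The gap per early stopper ranges from nil to several weeks. For a Day 22 stop with 31 fractions it is 40 days if follow-up runs to post-RT week 6, 12 days if it effectively ends at Visit 11, and 0 if it ends four weeks after the patient's own last application. These figures assume radiation starting on Day 8, five fractions a week and no interruptions. The documents do not support a total number affected, a distortion of AE incidence, or a direction of bias. The change is worth making before database lock because it alters what is tabulated and needs no new data.

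**What to change.** 1. State one upper bound for treatment-emergence and use it for fully and partly dated onsets in SAP 7.1.3.1 and 7.1.3.2. The final study visit for both would match the collection period. If 30 days after last dose is kept, 7.1.3.2 should compare month and year with that date instead of the last visit.
2. Reconcile the chosen bound with SAP 7, and amend the restriction in 7.1.1 so that whole-study tables are allowed.
3. Add to SAP 7.1.6.1 by-arm tables of all AEs and of all SAEs, including deaths, from first dose to the final visit. The 30-day tables may stay as the on-treatment view.
4. Reconcile Protocol 8.4.1, Protocol 9.5.1, footnote h and the post-RT week 6 label, so that the date of the final visit for a patient who stops lotion early is unambiguous.

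Cost: a few sentences, one programming cut-off and one or two extra tables, with no new data. The downside is that a few late events less likely to be drug-related enter the whole-study tables; SAP 7.1.6.1 already has a separate table for related events.
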